14.1.12 Determination of non-target lesion response

[figure not shown]
Table 14-2 Response criteria for non-target lesions

Response Criteria	Evaluation of non-target lesions
Complete Response (CR):	Disappearance of all non-target lesions. In addition, all lymph nodes assigned a non-target lesions must be non-pathological in size (< 10 mm short axis)
Partial Response (PR):	Unequivocal progression of existing non-target lesions. ¹
Non-CR/Non-PD:	Neither CR nor PD
Unknown (UNK)	Progression has not been documented and one or more non-target lesions have not been assessed or have been assessed using a different method than baseline.

¹. Although a clear progression of non-target lesions only is exceptional, in such circumstances, the opinion of the treating physician does prevail and the progression status should be confirmed later on by the review panel (or study chair).

Notes on non-target lesion response

- The response for non-target lesions is **CR** only if all non-target non-nodal lesions which were evaluated at baseline are now all absent and with all non-target nodal lesions returned to normal size (i.e. < 10 mm). If any of the non-target lesions are still present, or there are any abnormal nodal lesions (i.e. ≥10 mm) the response can only be ‘**Non-CR/Non-PD**’ unless any of the lesions was not assessed (in which case response is **UNK**) or there is unequivocal progression of the non-target lesions (in which case response is **PD**).

Unequivocal progression: To achieve “unequivocal progression” on the basis of non-target disease there must be an overall level of substantial worsening in non-target disease such that, even in presence of CR, PR or SD in target disease, the overall tumor burden has increased sufficiently to merit discontinuation of therapy. A modest “increase” in the size of one or more non-target lesions is usually not sufficient to qualify for unequivocal progression status. The designation of overall progression solely on the basis of change in non-target disease in the face of CR, PR or SD of target disease is therefore expected to be rare. In order for a PD to be assigned on the basis of non-target lesions, the increase in the extent of the disease must be substantial even in cases where there is no measurable disease at baseline. If there is unequivocal progression of non-target lesion(s), then at least one of the non-target lesions must be assigned a status of “Worsened”. Where possible, similar rules to those described in [Section 14.1.11](#) for assigning PD following a CR for the non-target lesion response in the presence of non-target lesions nodal lesions should be applied.

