3.2.1 Secondary endpoints

Efficacy endpoints based on radiological (and photographic when applicable) assessments of tumor burden will be derived using local (treating center's) radiologist's/ investigator's assessment.

For patients without event at the end of the study, data will be censored at the date of last adequate tumor assessment.

- Overall Response Rate (ORR) over the study period:
 - Overall response rate (ORR) is defined as the proportion of patients with best overall response of either complete response (CR) or partial response (PR) according to RECIST (version 1.1).
- Progression Free Survival (PFS) rate over the study period:
 - PFS rate is defined as the proportion of patients who have not had any documented progression or death due to any cause, according to RECIST (version 1.1).
- Clinical Benefit Rate (CBR) over the study period:
 - CBR rate is defined as the proportion of patients with best overall response of complete response (CR), partial response (PR) or stable disease (SD), with duration of 24 weeks or longer, according to RECIST (version 1.1).

For these three outcomes, in patients with non-measurable disease (bone metastases), the following is considered a disease progression: appearance of one or more new bone lytic lesions; appearance of one or more lesions outside of bone; unequivocal progression of existing bone lesions. Pathological fracture, new compression fracture, or complications of bone metastases will not be considered as evidence of disease progression unless one of the above criteria is fulfilled.

Changes from baseline in ECOG performance status will be described. Time to deterioration of ECOG performance status, from baseline will be assessed.

[figure not shown]
[figure not shown]
[figure not shown]
[figure not shown]

Table 3-1 Objectives and related endpoints

Objective	Endpoint	Analysis
Primary		
To evaluate the safety and tolerability profile of everolimus in post-menopausal women with HR positive, HER2 negative locally advanced or metastatic breast cancer after documented recurrence or progression following a non-steroidal aromatase inhibitor therapy in Novartis Oncology EGM countries.	Incidence of adverse events (AEs) by grade, serious adverse events (SAEs), changes from baseline in vital signs and laboratory results (hematology, blood chemistry, lipid profile) qualifying as AEs. All AEs will be assessed according to the Common Terminology Criteria (CTCAE), version 4.03.	Refer to Section 10.5

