14.1.7 Follow-up evaluation of target and non-target lesions

To assess tumor response, the sum of diameters for all target lesions will be calculated (at baseline and throughout the study). At each assessment response is evaluated first separately for the target (Table 14-1) and non-target lesions (Table 14-2) identified at baseline. These evaluations are then used to calculate the overall lesion response considering both the target and non-target lesions together (Table 14-3) as well as the presence or absence of new lesions.

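### Protocol Table 14-2 labels unequivocal non-target progression as Partial Response and has no PD row, contradicting its own note and the tables that use it

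*Protocol*

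**What the plan says.** Section 14.1.7 sets the order of scoring: "At each assessment response is evaluated first separately for the target" lesions (Table 14-1) and for the non-target lesions (Table 14-2). The two results are then combined in Table 14-3, together with new lesions.

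Table 14-2 in Section 14.1.12 has four rows: CR, PR, Non-CR/Non-PD and UNK. The PR row is defined as "Unequivocal progression of existing non-target lesions". The row after it is defined as "Neither CR nor PD", so it relies on a PD category that the table does not contain.

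Other text says something different about the same finding:

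- Footnote 1, attached to the PR row, begins "Although a clear progression of non-target lesions only is exceptional", so it reads the row as progression.
- The note below the table covers the case where "there is unequivocal progression of the non-target lesions (in which case response is" PD.
- The paragraph on unequivocal progression in the same section says: "In order for a PD to be assigned on the basis of non-target lesions, the increase in the extent of the disease must be substantial".
- Table 14-3 (Section 14.1.14) and Table 14-4 (Section 14.1.25) both take a non-target PD and return an overall PD. Neither lists a non-target PR as an input.
- Section 3.2.1, for patients with bone metastases and no measurable disease, counts "unequivocal progression of existing bone lesions" as progression. Section 7.3 does the same.

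**The concern.** The error is in a criteria table that the appendix tells the assessor or programmer to use, and the printed label is the opposite of what is meant. If the label is followed, non-target progression enters Table 14-3 as something other than PD. A patient who has progressed can then keep an overall response of PR, SD or UNK.

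ORR, CBR and PFS are all built from local overall lesion responses (Section 10.6.1), and the protocol plans no central reading of scans for them. A missed PD would lengthen PFS, could carry a stable patient past the 24-week threshold for CBR, and could confirm a response that should not be confirmed. Disease progression is also listed among the reasons for ending everolimus (Sections 6.5 and 7.1.4). That is a further reason to reconcile the passages; this point takes no position on that rule.

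**Working it through.** There is no planned figure to reproduce. Section 10.7 describes a descriptive study without hypothesis tests, and the sample size of up to 400 has no derivation. The check is therefore a table lookup.

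**Step 1: apply the downstream tables under both readings.** Inputs are Table 14-3 (patients with target lesions) and Table 14-4 (non-target disease only). Assume no new lesion and unequivocal non-target progression at the assessment.

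| Target response | Overall response, non-target scored PR (as printed) | Overall response, non-target scored PD (as the note says) |
|---|---|---|
| CR | no matching row | PD |
| PR | PR | PD |
| SD | SD | PD |
| UNK | UNK | PD |
| PD | PD | PD |
| none (Table 14-4) | no matching row | PD |

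The PR and SD lines arise because Table 14-3 accepts, for those target states, any non-target result other than PD or UNK. Target CR has no match because, without a new lesion or a PD, it is paired only with a non-target CR, Non-CR/Non-PD or UNK. Table 14-4 has no PR entry.

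So the printed label gives an overall response in one of five target states (PR). It hides progression in two more (SD, UNK), gives no answer in one (CR), and changes nothing in the last (PD).

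**Step 2: carry this to the endpoints.**

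- *ORR.* Section 10.6.1.1 requires two determinations of PR or better at least 4 weeks apart. Suppose target PR at weeks 10 and 20, with unequivocal non-target progression at week 20. The printed label gives PR, PR, a confirmed response. The note gives PR, PD, with no confirmation. Each such patient moves ORR by 100/N points: 100/400 = 0.25 at the planned maximum, and 100/198 = 0.51 at the 198 patients enrolled by 30 June 2014 (rationale for Amendment 2).
- *CBR.* Duration of stable disease runs from the start of treatment (Section 14.1.22; SAP Table 8.2.1). Suppose target SD with non-target progression at the week 20 scan, which falls between weeks 18 and 22 within its window. Read as PD, stable disease ends before 24 weeks. Read from the label, it can run to the next scan at weeks 28 to 32 and count as benefit.
- *PFS.* In the PR, SD and UNK lines the event is missed at that assessment, so the recorded event or censoring date may be later.

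**Step 3: how many patients.** The count is the number with unequivocal non-target progression, no new lesion and no target PD, multiplied by the share of those scored from the label rather than the note. The documents give neither quantity. Section 14.1.12 expects overall progression based only on non-target change, alongside target CR, PR or SD, to be rare. That expectation does not cover patients with no target disease.

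**The case against.** The strongest reply is that nobody could misread the row. Its own definition says progression, its footnote says progression, the note directly below gives PD, and both downstream tables expect PD. An assessor would have to read a description of unequivocal progression and record a response. This largely stands: only one rule is intended, and the documents do not support the inference that the sponsor chose a different one.

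A second reply is that safeguards exist. Section 14.1.31 provides data review reports for assessments where the investigator's opinion differs from the programmed response, and these may be queried. Footnote 1 asks for later confirmation of progression seen only in non-target lesions. This stands in part: the mismatch review helps only if the programmed rule uses PD, and Table 14-2 as printed does not supply it.

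Two stronger readings are tempting, and the documents do not support them:

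- A reader might infer that bone-only patients lose their main route to progression. Sections 3.2.1 and 7.3 give these patients their own rule with three routes, two of which are new lesions and do not depend on Table 14-2. Under the printed label their result is undefined, not a response.
- A reader might infer that each misread delays PD by at least one full 10-week interval. With windows of ±2 weeks, scans at weeks 12 and 18 are 6 weeks apart (18 − 12). Table 7-1 also requires a RECIST evaluation of scans done outside the schedule, and a death ends PFS sooner.

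**Conclusion.** The contradiction is real. Table 14-2 is wrong as printed, because it is an operative table, mislabels progression and omits the PD category that its next row and Tables 14-3 and 14-4 need. It is an internal labelling error, not a design decision.

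Its reach is limited. Safety is the primary endpoint (Section 3.1.1), and the exposed endpoints are secondary and descriptive. A reader might conclude that non-target progression will generally be counted as response. That needs target PR at the same assessment and, for ORR, that the misread assessment supplies one of the two required determinations. Nothing in the documents shows that any patient has been misclassified.

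This rests on two assumptions: that the row label in the text matches the original PDF, which should be checked although the rows and footnote look intact, and that Appendix 1 is current, as Amendment 1 indicates by updating it to version 3.1.

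**What to change.** - Relabel the row Progressive Disease (PD), to agree with the protocol's own note and Tables 14-3 and 14-4. This changes one row heading. Section 12.1 requires a written amendment for any protocol change, so it can travel with the next one.
- Notify sites that the note under Table 14-2 states the intended reading.
- Confirm that the programmed overall lesion response takes unequivocal non-target progression as PD.
- Before database lock, use the mismatch review in Section 14.1.31 to query any assessment where a non-target lesion is recorded as Worsened but the overall lesion response is not PD. This should be a query and not a recode, because Section 14.1.12 says that a modest increase usually does not qualify as unequivocal progression.

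A search for non-target entries of PR may find no field to search. SAP Listing 13.2 shows a status for each non-target lesion and Listing 13.4 the overall lesion response; neither shows a non-target response category. The query above uses data those listings show as collected, so the cost is one edit check and the time to resolve the queries.

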14.1.13 New lesions

The appearance of a new lesion is always associated with Progressive Disease (PD) and has to be recorded as a new lesion in the New Lesion CRF page.

- If a new lesion is **equivocal**, for example because of its small size, continued therapy and follow-up evaluation will clarify if it represents truly new disease. If repeat scans confirm there is definitely a new lesion, then progression should be declared using the date of the first observation of the lesion.
- If new disease is observed in a region which was **not scanned at baseline** or where the particular baseline scan is not available for some reason, then this should be considered as a PD. The one exception to this is when there are no baseline scans at all available for a patient in which case the response should be UNK, as for any of this patient's assessment (see [Section 14.1.14](#)).
- A **lymph node is considered as a “new lesion”** and, therefore, indicative of progressive disease if the short axis increases in size to ≥ 10 mm for the first time in the study plus 5 mm absolute increase.

FDG-PET: can complement CT scans in assessing progression (particularly possible for ‘new’ disease). See [Section 14.1.5](#).

14.1.14 Evaluation of overall lesion response

The evaluation of overall lesion response at each assessment is a composite of the target lesion response, non-target lesion response and presence of new lesions as shown below in [Table 14-3](#).

Table 14-3 Overall lesion response at each assessment

Target lesions	Non-target lesions	New Lesions	Overall lesion response
CR	CR	No	CR ¹
CR	Non-CR/Non-PD ³	No	PR
CR, PR, SD	UNK	No	UNK
PR	Non-PD and not UNK	No	PR ¹
SD	Non-PD and not UNK	No	SD ^{1, 2}
UNK	Non-PD or UNK	No	UNK ¹
PD	Any	Yes or No	PD
Any	PD	Yes or No	PD
Any	Any	Yes	PD

1. This overall lesion response also applies when there are no non-target lesions identified at baseline.
2. Once confirmed PR was achieved, all these assessments are considered PR.
3. As defined in [Section 14.1.7](#).

If there are no baseline scans available at all, then the overall lesion response at each assessment should be considered Unknown (UNK).

If the evaluation of any of the target or non-target lesions identified at baseline could not be made during follow-up, the overall status must be ‘unknown’ unless progression was seen.

In some circumstances it may be difficult to distinguish residual disease from normal tissue.

When the evaluation of complete response depends on this determination, it is recommended that the residual lesion be investigated (fine needle aspirate/biopsy) to confirm the CR.

14.1.15 Efficacy definitions

The following definitions primarily relate to patients who have measurable disease at baseline.

[Section 14.1.25](#) outlines the special considerations that need to be given to patients with no measurable disease at baseline in order to apply the same concepts.

14.1.16 Best overall response

The best overall response is the best response recorded from the start of the treatment until disease progression/recurrence (taking as reference for PD the smallest measurements recorded since the treatment started). In general, the patient's best response assignment will depend on the achievement of both measurement and confirmation criteria.

The best overall response will usually be determined from response assessments undertaken while on treatment. However, if any assessments occur after treatment withdrawal the protocol should specifically describe if these will be included in the determination of best overall response and/or whether these additional assessments will be required for sensitivity or supportive analyses. As a default, any assessments taken more than 30 days after the last dose of study treatment will not be included in the best overall response derivation. If any alternative cancer therapy is taken while on study any subsequent assessments would ordinarily be excluded from the best overall response determination. If response assessments taken after withdrawal from study treatment and/or alternative therapy are to be included in the main endpoint determination, then this should be described and justified in the protocol.

Where a study requires confirmation of response (PR or CR), changes in tumor measurements must be confirmed by repeat assessments that should be performed not less than 4 weeks after the criteria for response are first met.

Longer intervals may also be appropriate. However, this must be clearly stated in the protocol.

The main goal of confirmation of objective response is to avoid overestimating the response rate observed. In cases where confirmation of response is not feasible, it should be made clear when reporting the outcome of such studies that the responses are not confirmed.

- For non-randomized trials where response is the primary endpoint, confirmation is needed.
- For trials intended to support accelerated approval, confirmation is needed
- For all other trials, confirmation of response may be considered optional.
- The best overall response for each patient is determined from the sequence of overall (lesion) responses according to the following rules:
- CR = at least two determinations of CR at least 4 weeks apart before progression where confirmation required or one determination of CR prior to progression where confirmation not required
- PR = at least two determinations of PR or better at least 4 weeks apart before progression (and not qualifying for a CR) where confirmation required or one determination of PR

Overall lesion responses of CR must stay the same until progression sets in, with the exception of a UNK status. A patient who had a CR cannot subsequently have a lower status other than a PD, e.g. PR or SD, as this would imply a progression based on one or more lesions reappearing, in which case the status would become a PD.

Once an overall lesion response of PR is observed (which may have to be a confirmed PR depending on the study) this assignment must stay the same or improve over time until progression sets in, with the exception of an UNK status. However, in studies where confirmation of response is required, if a patient has a single PR ($\geq 30\%$ reduction of tumor burden compared to baseline) at one assessment, followed by a $< 30\%$ reduction from baseline at the next assessment (but not $\geq 20\%$ increase from previous smallest sum), the objective status at that assessment should be SD. Once a confirmed PR was seen, the overall lesion response should be considered PR (or UNK) until progression is documented or the lesions totally disappear in which case a CR assignment is applicable. In studies where confirmation of response is not required after a single PR the overall lesion response should still be considered PR (or UNK) until progression is documented or the lesion totally disappears in which case a CR assignment is applicable.

Example: In a case where confirmation of response is required the sum of lesion diameters is 200 mm at baseline and then 140 mm - 150 mm - 140 mm - 160 mm - 160 mm at the subsequent visits. Assuming that non-target lesions did not progress, the overall lesion response would be PR - SD - PR - PR - PR. The second assessment with 140 mm confirms the PR for this patient. All subsequent assessments are considered PR even if tumor measurements decrease only by 20% compared to baseline (200 mm to 160 mm) at the following assessments.

If the patient progressed but continues study treatment, further assessments are not considered for the determination of best overall response.

Note: these cases may be described as a separate finding in the CSR but not included in the overall response or disease control rates.

- The best overall response for a patient is always calculated, based on the sequence of overall lesion responses. However, the overall lesion response at a given assessment may be provided from different sources: Investigator overall lesion response
- Central Blinded Review overall lesion response
- Novartis calculated overall lesion response (based on measurements from either Investigator or Central Review)

The primary analysis of the best overall response will be based on the sequence of investigator/central blinded review/calculated (investigator)/calculated (central) overall lesion responses.

Based on the patients' best overall response during the study, the following rates are then calculated:

Overall response rate (ORR) is the proportion of patients with a best overall response of CR or PR. This is also referred to as 'Objective response rate' in some protocols or publications.

Disease control rate (DCR) is the proportion of patients with a best overall response of CR or PR or SD.

Another approach is to summarize the progression rate at a certain time point after baseline. In this case, the following definition is used:

Early progression rate (EPR) is the proportion of patients with progressive disease within 8 weeks of the start of treatment.

The protocol should define populations for which these will be calculated. The timepoint for EPR is study specific. EPR is used for the multinomial designs of [Dent and Zee \(2001\)](#) and counts all patients who at the specified assessment (in this example the assessment would be at 8 weeks \pm window) do not have an overall lesion response of SD, PR or CR. Patients with an unknown (UNK) assessment at that time point and no PD before, will not be counted as early progressors in the analysis but may be included in the denominator of the EPR rate, depending on the analysis population used. Similarly when examining overall response and disease control, patients with a best overall response assessment of unknown (UNK) will not be regarded as "responders" but may be included in the denominator for ORR and DCR calculation depending on the analysis population (e.g. populations based on an ITT approach).

